5.3.2. Handling of incomplete dates

5.3.2.1. Adverse events

Incomplete AE-related dates will be imputed in a conservative manner, as follows:

- If the AE onset date is missing completely, then the onset date will be replaced by the start of study treatment.
- If only the day part of the AE onset date is missing, but the month and year are equal to the start of study treatment, then the AE onset date will be replaced by the start of study treatment. For example, if the AE onset date is --/NOV/2014, and study treatment start date is 14/NOV/2014, then the imputed AE onset date will be 14/NOV/2014.
- If both the day and month of the AE onset date are missing but the onset year is equal to the start of study treatment, then the onset date will be replaced by the start of study treatment. For example, if AE onset date is --/---/2013, and study treatment start date is 18/JAN/2013, then the imputed AE onset date will be 18/JAN/2013.
- In all other cases the missing onset day or missing onset month will be replaced by 1.
- Incomplete stop date will be replaced by the last day of the month (if day is missing only) if not resulting in a date later than the date of patient's death. In the latter case the date of death will be used to impute the incomplete stop date.

• In all other cases the incomplete stop date will not be imputed. If stop date of AE is after the date of cut-off then the outcome of AE will be ongoing at cut-off.

5.3.2.2. Prior and concomitant medications

Incomplete prior/concomitant medication dates will be imputed as follows:

- If the medication date is missing completely, then the medication date will be replaced by the start of study treatment.
- If the day of medication date is missing, but the month and year are equal to the start of study treatment, then the medication date will be replaced by the start of study treatment. For example, if the medication start date is --/NOV/2014, and study treatment start date is 15/NOV/2014, then the imputed medication start date will be 15/NOV/2014.
- If both the day and month of medication start date are missing but the start year is equal to the start of study treatment, then the medication date will be replaced by the start of study treatment. For example, if the medication start date is --/---/2013, and study treatment start date is 20/JAN/2013, then the imputed medication start date will be 20/JAN/2013.
- In all other cases the missing medication day or missing medication month will be replaced by 1.
- Incomplete stop date will be replaced by the last day of the month (if day is missing only) if not resulting in a date later than the date of patient's death. In the latter case the date of death will be used to impute the incomplete stop date.
- In all other cases the incomplete medication stop date will not be imputed.

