8.1.6 Prior and Concomitant Medications

Prior and concomitant medications will be captured separately for BCC (facial) and other indications.

All medications ongoing in the 12 months prior to Baseline or ongoing at any time during the study will be recorded in the eCRF. The start date for all medications that were started during the study period must be reported. Likewise, the end date for all medications that were discontinued during the study period must be captured.

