4.1. Safety Population

The safety analysis set will include all patients who had at least one application of study treatment. The primary population for analysis of safety and efficacy will be the safety population.

Subgroup analysis will be done for subjects with history of oral or topical HHI in past 6 months – Yes/No. This will be determined based on the group they were randomized in the parent study (i.e. either 201 or 301) and the previous and concomitant medication pages.

The following efficacy assessments will be analyzed for the forementioned subgroups:

- The number of facial BCCs removed by surgery (per Investigator determination) and histologically verified as BCC; from Baseline to Month 12
- The number of facial BCCs removed by surgery (per Investigator determination) from Baseline to Month 12
- Change from Baseline to Month 12 in the total number of facial lesions suspicious for BCC

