4.2. Other Population

4.2.1. Per-protocol Population

The Per-Protocol set (PPS) will include all subjects in the Safety population who have no major Protocol Deviations (PDs). The final criteria for the PPS will be determined when all data on PDs are available through a Data Review Meeting (DRM). Data for all patients will be assessed to determine if patients meet the criteria for inclusion in each analysis population prior to releasing the database (i.e. Database Lock) and classifications will be documented per TFS's (or Sponsor's) standard operating procedures. Patients who meet any of the following criteria may be excluded from the PP analysis set:

- Patient with any major protocol violations in regards to inclusion/exclusion criteria
- Patient not completing 12 months of treatment with 80% 120% treatment compliance (see Section 6.3.3)
- Patient taking any prohibited concomitant medications.

All PDs will be reported to PellePharm and recorded throughout the study. A tabulation of PDs will be included in the final study report.

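### The SAP's date-imputation rules move a missing AE onset or medication start to the first application day without checking a known earlier stop date

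*SAP*

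**What the plan says.** **Imputation of starts.** SAP 5.3.2.2 says of medications: "If the medication date is missing completely, then the medication date will be replaced by the start of study treatment". The examples in the bullets that follow show that the start date is meant. SAP 5.3.2.1 says of AEs: "If the AE onset date is missing completely, then the onset date will be replaced by the start of study treatment". In both sections a start with only the day missing, in the month of first application, also becomes the first application date. So does a start known only to the year of first application. Any other partial start has its missing parts set to 1.

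**Imputation of stops.** A stop date with only the day missing becomes the last day of that month, or the date of death if earlier. For medications, SAP 5.3.2.2 then adds: "In all other cases the incomplete medication stop date will not be imputed".

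**What is collected.** Protocol 8.1.6 sets the scope: "All medications ongoing in the 12 months prior to Baseline or ongoing at any time during the study will be recorded in the eCRF". It then fixes which dates are mandatory: "The start date for all medications that were started during the study period must be reported" and "Likewise, the end date for all medications that were discontinued during the study period must be captured". SAP 6.3.1.3 repeats these requirements without extending them to drugs used only before the study. For AEs, Protocol 11.1.2 starts collection at consent and lists onset and end dates for every event.

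**Where the dates are used.** SAP 6.4.2 and 5.2.3 make an AE treatment-emergent if its onset falls between first application and 30 days after the last. SAP 6.4.2.1 splits AEs into those before treatment and those that are treatment-emergent. SAP 4.1 derives the HHI subgroup (use in the past 6 months, Yes/No) from the parent-study randomised group and "the previous and concomitant medication pages". SAP 4.2.1 gives as one possible reason for exclusion from the per-protocol set: "Patient taking any prohibited concomitant medications".

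**The concern.** Moving an undated start to Day 1 is a sensible conservative convention when the record might still have been running on Day 1. It is wrong when the stop date shows that the record had already ended. The SAP does not separate the two cases, and it does not define prior or concomitant medication, so the programmer has no rule for repairing the resulting record.

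Two outputs are exposed. The first is the treatment-emergent AE tables, which serve the primary objective: an event that was over before the first application can be counted as emergent. The second is the medication data. There a record can end before it starts, and a prior drug with no dates becomes an open-ended record from Day 1. If that drug is a non-study HHI, the subject's entry in the only planned subgroup may rest on an invented date.

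**Working it through.** The plan gives no figure to reproduce. The check applies the written rules literally to example records. The calendar dates below are assumptions chosen for illustration.

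**1. Adverse event.** Inputs: onset --/NOV, stop 5 NOV, first application 15 NOV. Protocol 8.1 allows up to 30 days between Screening and Baseline, so an event can begin after consent and end before Day 1.
- The day is missing and the month and year match first application, so imputed onset = 15 NOV.
- Onset minus stop = 15 − 5 = 10 days, so the event starts 10 days after it ended.
- 15 NOV is the first day of the on-treatment period, so the event meets the onset definition in SAP 6.4.2. It had ended before any drug was applied.
- By contrast, onset --/OCT with the same first application becomes 1 OCT and is correctly pre-treatment. The fault is confined to wholly missing onsets and to partial onsets in the month or year of first application.

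**2. Medications, with Day 1 assumed to be 15 Jul 2020.** The SAP gives no definition, so two plausible ones are tried: concomitant if the start is on or after Day 1, and concomitant unless the stop is before Day 1.

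| Recorded start | Recorded stop | Imputed start | Stop used | By start date | By stop date |
|---|---|---|---|---|---|
| none | none | 15 Jul 2020 | blank | concomitant | concomitant |
| none | 15 Mar 2020 | 15 Jul 2020 | 15 Mar 2020 | concomitant | prior |
| none | Mar 2020 | 15 Jul 2020 | 31 Mar 2020 | concomitant | prior |
| none | 2020 only | 15 Jul 2020 | blank | concomitant | concomitant |
| none | 1 Oct 2020 | 15 Jul 2020 | 1 Oct 2020 | concomitant | concomitant |
| 2020 only | none | 15 Jul 2020 | blank | concomitant | concomitant |

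In rows 2 and 3 the stop precedes the start, and the class depends on which definition the programmer picks. In rows 1 and 4 a drug that ended before the study reads as concomitant under both definitions. Row 5 is classed correctly.

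**3. HHI subgroup.** Take an HHI with no start date, stop 31 May 2020 and first application 15 Nov 2020.
- The imputed start is 15 Nov 2020. The gap from the stop is 30 (Jun) + 31 (Jul) + 31 (Aug) + 30 (Sep) + 31 (Oct) + 15 (Nov) = 168 days.
- With the SAP's conversion of 30.4375 days per month, 6 months = 6 × 30.4375 = 182.6 days. Since 168 < 182.6, the stop date still places use inside the window. The record is impossible, but the subgroup answer (Yes) can be recovered.
- With no stop date either, the answer cannot be recovered. The only date on the record is the imputed Day 1. Whether the subject is Yes or No then depends on how the window is programmed, not on when the drug was used.

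**The case against.** Several stronger readings are tempting, and the documents do not support them.

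- *The medication pages alone define the HHI subgroup.* They do not. SAP 4.1 also uses the parent-study randomised group, so patidegib given in Study 201 or 301 is identified without these dates. Only non-study HHI use known solely from the medication pages is exposed.
- *Every prior drug with a missing start becomes concomitant.* This is certain only when the stop is absent or known only to the year. With a usable pre-study stop, the class turns on a definition that the SAP does not give.
- *Missing dates are the norm by design.* Protocol 8.1.6 makes some dates mandatory; it does not say that the others go uncollected. The eCRF may collect them or carry a flag for drugs already stopped, and a site needs a rough idea of timing to apply the 12-month recording rule.
- *Subjects will be wrongly dropped from the per-protocol set.* SAP 4.2.1 says that such patients may be excluded and leaves the final criteria to a Data Review Meeting. The list of excluded drugs is not visible in the available text, so it cannot be confirmed that an HHI is on it.
- *The AE tables will be inflated.* AE dates are not optional under Protocol 11.1.2, and the event must fall in a short window. Few such events should arise, possibly none.

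It is also fair that all analyses are descriptive and that the Safety population is primary. These points limit how often the fault would occur and how far it would reach. None makes the rule correct for a record whose stop date precedes the first application.

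**Conclusion.** The point holds as a defect in the written rules. For an AE or a medication with a known stop before first application, and a start that is missing or partial in the month or year of first application, SAP 5.3.2.1 and 5.3.2.2 produce a start after the end. For AEs, the result meets the treatment-emergent onset definition and puts the event on the wrong side of the split in SAP 6.4.2.1. A prior medication with neither date, which the protocol permits, becomes open-ended from Day 1 and could misclassify non-study HHI use.

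The size cannot be stated. The documents do not give the number of affected records and do not show the eCRF. The gaps of 10 and 168 days illustrate single records and do not estimate frequency. A reader might infer that the HHI subgroup or the per-protocol set is unreliable as a whole; the documents do not support that. The change is worth making because the rule is wrong where it applies, it touches the primary safety tables, and the repair is cheap.

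**What to change.** Amend SAP 5.3.2.1 and 5.3.2.2 as follows.

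1. Impute an onset or start to the first application date only if the stop date is missing, or on or after first application, and the record is not otherwise known to have ended before the study.
2. Otherwise cap the imputed onset or start at the known stop date, and class the record as prior (for AEs, not treatment-emergent). If the record is known to have ended before the study but has no stop date, leave the start missing and class it as prior.
3. Define prior medication as one whose stop date is before first application, and concomitant as all others.
4. For any non-study HHI record, query at least the month and year of last use, so that the 6-month status does not rest on an imputed date.

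Items 1 to 3 cost a few lines of SAP text and a small programming change. Item 4 asks for slightly more than Protocol 8.1.6 makes mandatory, but it concerns one drug class and should mean only a small number of data queries.

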5.3.2.3. Exposure

No imputation will be done for first IP application date. Date of last IP application of study drug, if unknown or partially unknown, will be imputed as follows:

- If the last date of study drug is completely missing and there is no End of Treatment eCRF page and no death date, the date of last contact will be the last IP application date
- If the last date of study drug is completely or partially missing and there is an End of Treatment eCRF page available (within the cut-off date), then imputed last IP application date is:
 - = 31DECYYYY, if only Year is available and Year < Year of EOT date
 - = Last day of the month, if both Year and Month are available and Year = Year of EOT date and Month < the month of EOT date
 - = EOT date, for all other cases

5.3.3. Imputation rules for date of last contact

The date of last contact will be derived for patients at the analysis cut-off using the latest complete date among the following:

- All patient assessment dates (blood draws (laboratory), vital signs, performance status)
- AE start and end dates
- Study drug start and end dates
- Randomization date
- Withdrawal of consent date

Only dates associated with actual examinations of the patient will be used in the derivation.

6. ANALYSES AND SUMMARIES

6.1. Primary Endpoints

6.1.1. Safety and Tolerability.

Safety and tolerability are the primary objectives of this study and will be evaluated by reviewing adverse events (see Section 6.4.2), treatment discontinuations and dermal safety and tolerability (see Section 6.4.1).

6.1.1.1. Primary analysis

No inferential tests will be performed. Data will be summarized through descriptive statistics only.

6.2. Secondary Endpoint(s)

6.2.1. Safety endpoints

See Section 6.4.

6.2.2. Efficacy endpoints

The efficacy endpoints are:

- 1. The number of facial BCCs removed by surgery (per Investigator determination) and histologically verified as BCC; from Baseline to Month 12.
- 2. The number of facial BCCs removed by surgery (per Investigator determination) and histologically verified as BCC; from Baseline to Month 6.
- 3. The number of facial BCCs removed by surgery (per Investigator determination) from Baseline to Month 12.
- 4. The number of facial BCCs removed by surgery (per Investigator determination) from Baseline to Month 6.
- 5. Change from Baseline to Month 12 in the total number of facial lesions suspicious for BCC.

- 6. Count of facial lesions suspicious for BCC over time.
- 7. aBCCdex change in lesion score from Baseline to Month 12.

All efficacy assessments will be summarized descriptively by visit, depending on the nature of the variable. Changes from Baseline will also be displayed.

6.2.3. Exploratory Endpoints

The exploratory endpoints will investigate PROs:

- 1. Change in aBCCdex Worry About Future Lesions scale score from Baseline to Month 12.
- 2. Change in aBCCdex Mental Health scale score from Baseline to Month 12.
- 3. Change in aBCCdex Social/Relationships scale score from Baseline to Month 12.
- 4. Change in aBCCdex Life Impact scale score from Baseline to Month 12.
- 5. Change in Dermatology Life Quality Index (DLQI) total score from Baseline to Month 12
- 6. Shift in EuroQol (Quality of Life) using 5 levels (EQ-5D-5L) from baseline to Month 12
- 7. Change in EQ-5D-5L Visual Analog Scale (VAS) from Baseline to Month 12

A shift table will be presented for changes from baseline of the EQ-5D-5L dimension scores. Additionally, the VAS Scores will be summarized descriptively by visit.

6.2.4. Pharmacokinetic endpoints

Not applicable

6.3. Baseline and Other Summaries and Analyses

6.3.1. Baseline summaries

The following analyses will be based on the Safety population.

6.3.1.1. Demographic characteristics

Demographic characteristics and physical measurements will be summarized using the following information from screening visit in the 'Demographics' eCRF page.

- Demographic characteristics
 - Gender: Male, Female
 - Race: White, Black or African American, Asian, American Indian or Alaska Native, Native Hawaiian or other Pacific Islander, Other, Unknown
 - Ethnicity: Hispanic/Latino (Yes/No)

- Age (years): summary statistics
- Geographic Region:
 - United States + Canada
 - United Kingdom + European Union
- Physical measurements
 - Height (cm)
 - Weight (kg)
 - Body Mass Index (BMI) (kg/m²)
- Method of contraception
- Fertility

Demograhic characteristics and physical measurements will be summarized by descriptive statistics. All demographics data will be listed for the safety set.

6.3.1.2. Medical history

Medical history will be coded using the most current available version of Medical Dictionary for Regulatory Activities (MedDRA) and will be summarized from the 'Medical History' eCRF page. Medical history will be summarized as the numbers and percentages of patients by MedDRA preferred term (PT) as event category and MedDRA primary system organ class (SOC) as summary category. Each patient will be counted only once within each PT or SOC.

Medical history will be displayed in terms of frequency tables ordered by primary SOC and PT in alphabetical order.

6.3.1.3. Prior and concomitant medications/therapies

Prior and concomitant medications/therapies will be captured separately for BCC (facial) and other indications.

All medications ongoing in the 12 months prior to Baseline or ongoing at any time during the study will be recorded in the eCRF. The start date for all medications that were started during the study period must be reported. Likewise, the end date for all medications that were discontinued during the study period must be captured.

6.3.2. Study conduct and patient disposition

The following analyses will be performed based on the Safety population.

6.3.2.1. Patient disposition

The percentages below will be calculated based on the number of patients in the Safety population.

- Total number of patients enrolled
- Number and percentage of enrolled patients in each of the analysis populations defined in Section 4
- Number of enrolled patients who discontinued from the study and the main reason for discontinuation
- Number and percentage of enrolled patients who discontinued study treatment overall and by the main reason for discontinuation of study treatment

Additionally, Time to Treatment Discontinuation will be graphically displayed using Kaplan-Meier curves.

6.3.2.2. Protocol deviations

All protocol violations that impact the safety of the patients and/or the conduct of a study and/or its evaluation will be reported. These include:

- Patients who are treated on the study despite not satisfying the inclusion criteria
- Patients who develop withdrawal criteria whilst on the study but are not withdrawn
- Patients who receive an excluded concomitant medication
- Patient not completing 12 months of treatment within 80% 120% treatment compliance (See section 6.3.3)
- Deviations from GCP

The identification of these and other CSR-reportable deviations will be based on the inclusion/exclusion criteria or other criteria presented in the protocol.

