7.3 Study Drug Discontinuation

The Investigator has the right to permanently discontinue IP application of a subject at any time if in their opinion the continuation of the IP is deleterious to the subject's health or discontinuation is in the subject's best interest. If the subject becomes pregnant, IP will be discontinued immediately.

If, for any reason, a subject is discontinued during the treatment period prior to the Exit Visit, evaluations should be performed at the time of early termination and the reason for termination should be recorded in the end of study source documentation. At the 30 day follow up additional information may be collected. All data gathered on the subject will be made available to PellePharm.

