9.3 Protocol Deviations

A PD is any change, divergence, or departure from the study design or procedures defined in the protocol. Major PDs are a subset of PDs that might significantly affect the completeness, accuracy, and/or reliability of the study data or that might significantly affect a subject's rights, safety, or well-being (FDA sheets and notices). If a major (important) PD has been identified, it should be communicated to and discussed with the Medical Monitor. A corrective and preventative action (CAPA) plan may be required to be instituted in the case of major PDs at the site. In the event of recurring major PDs, the site enrollment may be halted by the Medical Monitor, in consultation with PellePharm, until a CAPA plan has been instituted and the issue(s) resolved. PDs should be reported on at least an annual basis to the Central IRB or the site's local IRB.

For IP received undamaged, IP will be inventoried and the IP inventory/accountability log completed.

The subject will return all IP gel tubes (used, partially used, and/or unused) at their subsequent study visit. If any IP gel tubes are lost or damaged between clinic visits, additional IP may be provided to the subject. The goal is to ensure that the subject has an adequate supply of IP to be able to administer all scheduled treatments.

Refer to the Pharmacy Manual for additional details about administration requirements, IP supply, and accountability procedures.

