5.2. General Methods

Endpoints will be summarized based on either the Safety or the PP analysis sets.

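### SAP 6.3.2.2 counts stopping before 12 months as a protocol violation whatever the reason, including stops that the protocol requires or permits

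*SAP*

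**What the plan says.** SAP 6.3.2.2 opens its list with "All protocol violations that impact the safety of the patients and/or the conduct of a study and/or its evaluation will be reported". One entry is "Patient not completing 12 months of treatment within" compliance limits of 80% and 120%; a range sign between the two percentages was probably lost in PDF reading, and I take it as 80% to 120%. No reason for stopping is exempt. Another entry covers subjects who meet withdrawal criteria but are kept in the study. The section closes by saying that deviations are identified from the eligibility criteria or other protocol criteria.

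SAP 4.2.1 defines the per-protocol (PP) set as Safety-population subjects without major deviations. It then lists conditions that may lead to exclusion, one being "Patient not completing 12 months of treatment with" the same compliance limits. On timing it says "The final criteria for the PPS will be determined when all data on PDs are available", through a Data Review Meeting, with subjects classified before database lock. SAP 6.3.3 computes compliance from the diary as doses taken over doses planned. It does not say what is planned for a subject who stops early.

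On the use of the sets, SAP 5.2 says "Endpoints will be summarized based on either the Safety or the PP analysis sets". SAP 4.1 makes the Safety population primary for safety and efficacy, and SAP 6.4 puts all safety summaries on it.

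Protocol 9.3 gives the definition: "A PD is any change, divergence, or departure from the study design or procedures defined in the protocol". Protocol 7.3 says "If the subject becomes pregnant, IP will be discontinued immediately" and lets the Investigator stop treatment permanently for the subject's health or best interest. Protocol 7.4 lets a subject withdraw freely, without giving a reason.

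**The concern.** A deviation table tells the reader how well the study was conducted. If every early stop goes into it, adverse-event stops, pregnancies and withdrawals of consent sit beside eligibility errors and prohibited medication, and the count no longer measures conduct.

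The PP entry raises a second issue. SAP 6.1.1 names treatment discontinuations as one of the things by which safety and tolerability, the primary objective, will be judged. A PP set from which early stoppers are removed is therefore selected on an outcome of treatment. Any efficacy summary on it describes subjects who tolerated the gel and chose to continue.

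**Working it through.** **Step 1. Is an early stop a departure from the protocol?**

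| Reason for stopping before month 12 | Protocol | Departure as defined in 9.3? | Caught by the SAP 6.3.2.2 entry read literally? |
|---|---|---|---|
| Pregnancy | 7.3: stop required | No | Yes |
| Investigator decision for the subject's health or interest | 7.3: permitted | No | Yes |
| Subject withdraws | 7.4: permitted | No | Yes |

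The protocol synopsis gives 12 months as the planned treatment duration. Nowhere does the protocol make completing 12 months, or 80% to 120% compliance, a criterion that a subject can breach. The entry therefore also fails the SAP section's own rule that deviations are identified from protocol criteria.

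**Step 2. Is the list consistent with itself?** Keeping a subject who meets withdrawal criteria is one entry. Withdrawing that subject before month 12 falls under another. Read literally, the subject is counted either way.

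**Step 3. What does the entry require?** Inputs: twice-daily use (SAP 2.2) and 30.4375 days per month (SAP 5.2.4).

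- Planned doses over 12 months = 12 × 30.4375 × 2 = 730.5.
- 80% limit = 0.8 × 730.5 = 584.4. 120% limit = 1.2 × 730.5 = 876.6.
- A perfectly adherent subject who stops at month t scores t/12 against a 12-month plan, or 100% against doses planned up to the stop.

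| Stop at month | Against 12-month plan | Against plan to the stop |
|---|---|---|
| 6 | 50% | 100% |
| 9 | 75% | 100% |
| 9.6 | 80% | 100% |
| 10 | 83.3% | 100% |
| 11 | 91.7% | 100% |

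Three readings follow:

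- (a) Complete 12 months and be compliant: every earlier stop fails.
- (b) Ratio only, with a 12-month denominator: adherent subjects who stop before month 0.8 × 12 = 9.6 fail.
- (c) Ratio only, with doses planned to the stop: no adherent early stopper fails.

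Reading (a) is closest to the words. Under (c) the 12-month phrase would do nothing.

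**Step 4. How many subjects?** The plan has no figure to reproduce: it states neither a discontinuation rate nor a PP-set size. For an assumed share d who stop before month 12, under reading (a) and with about 200 subjects (the stated maximum), the number listed = 200 × d and the largest PP set = 200 × (1 − d).

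| Assumed d | Listed as violators | PP set at most |
|---|---|---|
| 5% | 10 | 190 |
| 10% | 20 | 180 |
| 20% | 40 | 160 |
| 30% | 60 | 140 |
| 40% | 80 | 120 |

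Whatever d is, a PP set built on reading (a) contains nobody who stopped for an adverse event before month 12.

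**The case against.** The best defence has four parts.

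- **The text is softer than its harshest reading.** The entry combines duration with compliance and points to the compliance section, and the identification rule gives a basis for not classing a required stop as a violation. This is fair, and it is why the three readings are set out. But a programmer working from the list would have no exemption to apply.
- **The PP set is not fixed.** A reader might infer that it consists of completers only. The documents do not settle that: exclusion is permissive, the set rests on major deviations, and the Data Review Meeting decides. The completer description holds only if the criterion is applied as written.
- **Main results are protected.** A reader might also infer that a completer result could be picked as the headline after the data are seen. The documents do not support that. The Safety population is primary for efficacy as well as safety, subjects are classified before database lock, and there is no hypothesis testing. The loose wording in SAP 5.2 does not displace this, although it leaves the PP set without named endpoints. Discontinuations also appear separately, by main reason and with a Kaplan-Meier display (SAP 6.3.2.1), and adverse events leading to discontinuation are tabulated (SAP 6.4.2.2).
- **A completion requirement in a supportive set is defensible.** Two main efficacy endpoints count removals from Baseline to Month 12 (SAP 6.2.2), and nothing is imputed (SAP 5.3.1). If partial counts are used, a subject who stops at month 2 adds a low count only because follow-up was short. This stands: dropping the requirement from the PP set trades one bias for another.

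What remains is the violation list itself. Since disposition already reports discontinuations, their presence among the violations adds no information and mislabels subjects.

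**Conclusion.** The point holds for the deviation table. As written, SAP 6.3.2.2 classes protocol-required and protocol-permitted stops as violations, contrary to protocol 9.3 and to its own identification rule. For the PP set the point is conditional: if the 4.2.1 entry is applied as written, the set is one of compliant completers, selected on a component of the primary tolerability evaluation.

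The primary Safety-population results are untouched, so this is a matter of correct reporting, not of the study's main conclusions. The size depends on a discontinuation rate that the documents do not give. At an assumed 10% to 40% of 200, it is 20 to 80 subjects under the literal reading. Those counts are upper figures for mislabelling, because some early stops may accompany a real deviation.

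**What to change.** 1. **SAP 6.3.2.2:** remove early discontinuation from the violation list and report it only under disposition (6.3.2.1). Keep as a deviation only compliance outside 80% to 120%, computed over doses planned while the subject was on treatment. Because the protocol sets no such limit, say that it is an SAP-defined criterion.
2. **SAP 6.3.3:** state that denominator. Correct the cross-reference in the same edit: it cites 4.3.1, but the PP set is defined in 4.2.1.
3. **SAP 4.2.1:** if the 12-month requirement stays, call the set a compliant-completer set. If it goes, state how counts from shortened follow-up enter the Month 12 summaries.
4. **SAP 5.2:** state that the Safety population remains primary and that the PP set serves only as a supportive repeat of the efficacy endpoints.

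The cost is a small SAP edit and fewer reported deviations. No data collection changes, and no information on discontinuation is lost.
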